9.12 Extent of Exposure

The extent of exposure will be summarized by the number and proportion of randomized participants administered V114 or PCV13 and the number and proportion of randomized participants administered DTaP-IPV at each schedule.

10 SUPPORTING DOCUMENTATION AND OPERATIONAL CONSIDERATIONS

10.1 Appendix 1: Regulatory, Ethical, and Study Oversight Considerations

10.1.1 Code of Conduct for Clinical Trials

Merck Sharp and Dohme Corp., a subsidiary of Merck & Co., Inc. (MSD)

Code of Conduct for Interventional Clinical Trials

I. Introduction

A. Purpose

MSD, through its subsidiaries, conducts clinical trials worldwide to evaluate the safety and effectiveness of our products. As such, we are committed to designing, implementing, conducting, analyzing and reporting these trials in compliance with the highest ethical and scientific standards. Protection of participants in clinical trials is the overriding concern in the design of clinical trials. In all cases, MSD clinical trials will be conducted in compliance with local and/or national regulations (eg, International Council for Harmonisation Good Clinical Practice [ICH-GCP]) and in accordance with the ethical principles that have their origin in the Declaration of Helsinki.

B. Scope

Highest ethical and scientific standards shall be endorsed for all clinical interventional investigations sponsored by MSD irrespective of the party (parties) employed for their execution (eg, contract research organizations, collaborative research efforts). This Code is not intended to apply to trials that are observational in nature, or which are retrospective. Further, this Code does not apply to investigator-initiated trials, which are not under the full control of MSD.

II. Scientific Issues

A. Trial Conduct

1. Trial Design

Except for pilot or estimation trials, clinical trial protocols will be hypothesis-driven to assess safety, efficacy, and/or pharmacokinetic or pharmacodynamic indices of MSD or comparator products. Alternatively, MSD may conduct outcomes research trials, trials to assess or validate various endpoint measures, or trials to determine patient preferences, etc.

The design (ie, participant population, duration, statistical power) must be adequate to address the specific purpose of the trial. Participants must meet protocol entry criteria to be enrolled in the trial.

2. Site Selection

MSD selects investigative sites based on medical expertise, access to appropriate participants, adequacy of facilities and staff, previous performance in clinical trials, as well as budgetary considerations. Prior to trial initiation, sites are evaluated by MSD personnel to assess the ability to successfully conduct the trial.

3. Site Monitoring/Scientific Integrity

Investigative trial sites are monitored to assess compliance with the trial protocol and general principles of Good Clinical Practice (GCP). MSD reviews clinical data for accuracy, completeness, and consistency. Data are verified versus source documentation according to standard operating procedures. Per MSD policies and procedures, if fraud, scientific/research misconduct, or serious GCP-noncompliance is suspected, the issues

are investigated. When necessary, the clinical site will be closed, the responsible regulatory authorities and ethics review committees notified.

B. Publication and Authorship

Regardless of trial outcome, MSD commits to publish primary and secondary results of its registered trials of marketed products in which treatment is assigned, according to the prespecified plans for data analysis. To the extent scientifically appropriate, MSD seeks to publish the results of other analyses it conducts that are important to patients, physicians, and payers. Some early phase or pilot trials are intended to be hypothesis-generating rather than hypothesis testing, in such cases, publication of results may not be appropriate since the trial may be underpowered and the analyses complicated by statistical issues such as multiplicity.

MSD's policy on authorship is consistent with the recommendations published by the International Committee of Medical Journal Editors (ICMJE). In summary, authorship should reflect significant contribution to the design and conduct of the trial, performance or interpretation of the analysis, and/or writing of the manuscript. All named authors must be able to defend the trial results and conclusions. MSD funding of a trial will be acknowledged in publications.

III. Participant Protection

A. Ethics Committee Review (Institutional Review Board [IRB]/Independent Ethics Committee [IEC])

All clinical trials will be reviewed and approved by an IRB/IEC before being initiated at each site. Significant changes or revisions to the protocol will be approved by the ethics committee prior to implementation, except changes required urgently to protect participant safety that may be enacted in anticipation of ethics committee approval. For each site, the ethics committee and MSD will approve the participant informed consent form.

B. Safety

The guiding principle in decision-making in clinical trials is that participant welfare is of primary importance. Potential participants will be informed of the risks and benefits of, as well as alternatives to, trial participation. At a minimum, trial designs will take into account the local standard of care.

All participation in MSD clinical trials is voluntary. Participants enter the trial only after informed consent is obtained. Participants may withdraw from an MSD trial at any time, without any influence on their access to, or receipt of, medical care that may otherwise be available to them.

C. Confidentiality

MSD is committed to safeguarding participant confidentiality, to the greatest extent possible. Unless required by law, only the investigator, Sponsor (or representative), ethics committee, and/or regulatory authorities will have access to confidential medical records that might identify the participant by name.

D. Genomic Research

Genomic research will only be conducted in accordance with a protocol and informed consent authorized by an ethics committee.

IV. Financial Considerations

A. Payments to Investigators

Clinical trials are time- and labor-intensive. It is MSD's policy to compensate investigators (or the sponsoring institution) in a fair manner for the work performed in support of MSD trials. MSD does not pay incentives to enroll participants in its trials. However, when enrollment is particularly challenging, additional payments may be made to compensate for the time spent in extra recruiting efforts.

MSD does not pay for participant referrals. However, MSD may compensate referring physicians for time spent on chart review to identify potentially eligible participants.

B. Clinical Research Funding

Informed consent forms will disclose that the trial is sponsored by MSD and that the investigator or sponsoring institution is being paid or provided a grant for performing the trial. However, the local ethics committee may wish to alter the wording of the disclosure statement to be consistent with financial practices at that institution. As noted above, all publications resulting from MSD trials will indicate MSD as a source of funding.

C. Funding for Travel and Other Requests

Funding of travel by investigators and support staff (eg, to scientific meetings, investigator meetings, etc.) will be consistent with local guidelines and practices.

V. Investigator Commitment

Investigators will be expected to review MSD's Code of Conduct as an appendix to the trial protocol, and in signing the protocol, agree to support these ethical and scientific standards.

10.1.2 Financial Disclosure

Financial Disclosure requirements are outlined in the US Food and Drug Administration Regulations, Financial Disclosure by Clinical Investigators (21 CFR Part 54). It is the Sponsor's responsibility to determine, based on these regulations, whether a request for Financial Disclosure information is required. It is the investigator's/subinvestigator's responsibility to comply with any such request.

The investigator/subinvestigator(s) agree, if requested by the Sponsor in accordance with 21 CFR Part 54, to provide his/her financial interests in and/or arrangements with the Sponsor to allow for the submission of complete and accurate certification and disclosure statements. The investigator/subinvestigator(s) further agree to provide this information on a Certification/Disclosure Form, commonly known as a financial disclosure form, provided by the Sponsor. The investigator/subinvestigator(s) also consent to the transmission of this information to the Sponsor in the United States for these purposes. This may involve the transmission of information to countries that do not have laws protecting personal data.

10.1.3 Data Protection

Participants will be assigned a unique identifier by the Sponsor. Any participant records or datasets that are transferred to the Sponsor will contain the identifier only; participant names or any information that would make the participant identifiable will not be transferred.

The participant must be informed that his/her personal study-related data will be used by the Sponsor in accordance with local data protection law. The level of disclosure must also be explained to the participant.

The participant must be informed that his/her medical records may be examined by Clinical Quality Assurance auditors or other authorized personnel appointed by the Sponsor, by appropriate IRB/IEC members, and by inspectors from regulatory authorities.

10.1.3.1 Confidentiality of Data

By signing this protocol, the investigator affirms to the Sponsor that information furnished to the investigator by the Sponsor will be maintained in confidence, and such information will be divulged to the IRB, IEC, or similar or expert committee; affiliated institution and employees, only under an appropriate understanding of confidentiality with such board or committee, affiliated institution and employees. Data generated by this study will be considered confidential by the investigator, except to the extent that it is included in a publication as provided in the Publications section of this protocol.

10.1.3.2 Confidentiality of Participant Records

By signing this protocol, the investigator agrees that the Sponsor (or Sponsor representative), IRB/IEC, or regulatory authority representatives may consult and/or copy study documents to verify worksheet/CRF data. By signing the consent form, the participant agrees to this process. If study documents will be photocopied during the process of verifying worksheet/CRF information, the participant will be identified by unique code only; full names/initials will be masked prior to transmission to the Sponsor.

By signing this protocol, the investigator agrees to treat all participant data used and disclosed in connection with this study in accordance with all applicable privacy laws, rules and regulations.

10.1.3.3 Confidentiality of IRB/IEC Information

The Sponsor is required to record the name and address of each IRB/IEC that reviews and approves this study. The Sponsor is also required to document that each IRB/IEC meets regulatory and ICH GCP requirements by requesting and maintaining records of the names and qualifications of the IRB/IEC members and to make these records available for regulatory agency review upon request by those agencies.

10.1.4 Committees Structure

10.1.4.1 Internal Safety Data Assessment

Internal safety data assessment will be conducted at the interim analysis in this study. The assessment will be conducted by the members of Sponsor senior management, none of whom are directly associated with the conduct of the study. The member of internal safety data assessment will review the interim safety data that are unblinded at the subject level (Section 9.7). The information noted above will be used to make scientific decisions regarding the subsequent phases of V114 clinical development in Japanese pediatric. The results of the interim analysis will not be shared with the investigators and the project team until the end of the trial.

Specific details regarding responsibilities for internal safety data assessment will be described in separate internal procedures manual.

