6.3.3 Blinding

A double-blinding technique will be used. V114 and PCV13 will be prepared and/or dispensed by an unblinded pharmacist or unblinded qualified study personnel. The participant and the investigator who are involved in the clinical evaluation of the participants will remain blinded to the group assignments until end of the study.

Because the V114 and PCV13 have a different appearance, a member of the study site personnel will be unblinded for the purposes of receiving, maintaining, preparing and/or dispensing, and administering the study vaccine. Procedures for handling, preparing, and administering the unblinded vaccines are located in the Investigator Trial File Binder.

Due to differences in appearance, vaccine administration will be performed by unblinded study personnel who will have no contact with study participants other than administration of study vaccine, which includes all safety follow up procedures at each vaccination visit. Additionally, blinded site personnel and participant's parent/guardian will remain blinded such as not to be present in the same room or to be separated with a curtain when V114 and PCV13 are administered. Contact between participants and unblinded study personnel after each vaccination administration is strictly prohibited. Blinded study personnel will be responsible for all safety and immunogenicity follow-up procedures after study vaccine administration.

An unblinded Clinical Research Associate will monitor study vaccine accountability at the study site. All other Sponsor personnel or delegate(s) directly involved with the conduct of this study will remain blinded to the participant-level intervention assignment until the end of the study. See Section 8.1.11 for a description of the method of unblinding a participant during the study should such action be warranted.

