9.2 Responsibility for Analyses/In-house Blinding

The statistical analysis of the data obtained from this trial will be the responsibility of the Clinical Biostatistics department of the Sponsor.

This trial will be conducted as a double-blind trial under in-house blinding procedures. The Sponsor personnel, except those who are specifically designated to serve as unblinded roles (see Sections 6.3.3 and 9.7), will remain blinded to the treatment assignment of individual participants until the end of the trial. Site personnel, except those who are specifically designated to serve as unblinded roles (see Section 6.3.3), as well as participants and their parents/legal guardians, will also remain blinded until the end of the trial.

The Clinical Biostatistics department will generate the randomized allocation schedule for trial treatment assignment. Randomization will be implemented using interactive response technology (IRT) or its equivalent.

The planned interim analysis is described in Section 9.7. The results of the interim analysis will not be shared with the investigators prior to the completion of the trial. Subject-level unblinding will be restricted to the unblinded statistician and unblinded statistical programmer performing the interim analysis, as well as designated unblinded Sponsor personnel who will review safety data at the subject level. Group summaries will be reviewed by the Sponsor's trial team in order to make scientific decisions for future studies.

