9.7 Interim Analyses

An interim analysis will be performed after all participants continuing on the trial have completed the study visit at 1 month PD3 and the data (safety and immunogenicity) up to that point have become available. An unblinded statistician and a statistical programmer who are otherwise not involved in the trial or the project will have access to the treatment assignment of individual participants to analyze the data. The project team will review group level summary results but will not be unblinded at the subject level. Designated unblinded Sponsor personnel will review subject level safety data and communicate their recommendation regarding the future study to the project team in a manner that maintains subject level blinding for blinded Sponsor personnel. The information noted above will be used to make scientific decisions regarding the future study. The results of the interim analysis will not be

shared with the investigators until the end of the trial. The conduct of this trial will not be altered by the interim analysis.

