3.2 Responsibility for Analyses/In-house Blinding

The statistical analysis of the data obtained from this trial will be the responsibility of the Clinical Biostatistics department of the Sponsor.

This trial will be conducted as a double-blind trial under in-house blinding procedures. The Sponsor personnel, except those who are specifically designated to serve as unblinded roles (see Section 6.3.3 of the protocol, and Section 3.7), will remain blinded to the treatment assignment of individual participants until the end of the trial. Site personnel, except those who are specifically designated to serve as unblinded roles (see Section 6.3.3 of the protocol), as well as participants and their parents/legal guardians, will also remain blinded until the end of the trial.

The Clinical Biostatistics department will generate the randomized allocation schedule for trial treatment assignment. Randomization will be implemented using interactive response technology (IRT) or its equivalent.

The planned interim analysis is described in Section 3.7. The results of the interim analysis will not be shared with the investigators prior to the completion of the trial. Subject-level unblinding will be restricted to the unblinded statistician and unblinded statistical programmer performing the interim analysis, as well as designated unblinded Sponsor personnel who will review safety data at the subject level. Group summaries will be reviewed by the Sponsor's trial team in order to make scientific decisions for future studies.

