APPENDIX

Access control of study data and results at interim analysis

Access to the data and results of the interim analysis will be restricted (See [Section 3.7](#)). For this purpose, access to the study folders within the computing platform for analysis and reporting will be controlled as follows.

Table 5 Access granted by folder and membership

CPI region	TEST	PROD	PROD
Folder name (under “v114-pcv”)	prot028-ia	prot028-ia	prot028-ia-summary
Folder use	Develop analysis programs under blinded environment	Perform interim analysis under unblinded environment	Group summary results of interim analysis results posted
Project team	Y	N	Y
Unblinded statistician / unblinded statistical programmer / unblinded clinical scientist	Y	Y	Y
Designated unblinded Sponsor personnel for reviewing safety data	N/A	Y	N/A

Y = access granted, N = access not granted, N/A = not applicable
CPI = computing platform integration (computing platform for analysis and reporting)

“prot028-ia” folder in the TEST region

This folder will be used by the protocol statistical programmer and the protocol statistician to develop analysis programs. This will not require any information of the actual treatment allocation of individual participants (only dummy treatment codes will be used). Prior to the database lock for the interim analysis, the study team will review the “dry run” output that are generated using the available study data up to that point in combination with the dummy treatment codes. Review of the dry run output will be conducted using the associated “- clinical” folder.

“prot028-ia” folder in the PROD region

This folder will be used by the unblinded statistician and the unblinded statistical programmer to perform interim analysis. An unblinded clinical scientist will inform the unblinded statistician and the unblinded statistical programmer of any vaccination with incorrect product and/or route of administration. Based on this information, in combination with the exclusion from analysis memo created by the blinded study team members before the database lock for the interim analysis, the unblinded statistician or the unblinded statistical programmer will flag subjects and/or datapoints within the datasets for exclusion from analysis.

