All tables, listings and figures for the interim analysis will be generated in this folder by the unblinded statistician and the unblinded statistical programmer and will be provided with the designated Sponsor personnel who will review the safety data unblinded at the subject level. This will be performed using the associated “-clinical” folder.

“prot028-ia-sumamry” folder in the PROD region

After the database lock for the interim analysis is achieved, the unblinded statistician and the unblinded statistical programmer will post group level summary results to this folder for review by the project team. The protocol statistician will prepare the Early Results Memo based on the group level summary results using the tables posted in this folder.

It is the responsibility of the unblinded statistician to mask or remove part of the output before providing the output with the project team in order to avoid potential subject level unblinding. Examples include:

- AEs, disposition events, medical history, prior / concomitant medications observed in only one participant or in only one vaccination group
- minimum and maximum (e.g., baseline body weight).

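### Do the conflicting statements on who sees the interim results, and who is unblinded for them, put any result of the trial at risk?

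*Combined protocol and SAP*

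**What the plan says.** **Who sees interim results.** Protocol 10.1.4.1 describes a safety review by senior sponsor management who are not directly associated with running the study. It cites section 9.7 for that review and ends: "The results of the interim analysis will not be shared with the investigators and the project team until the end of the trial". Section 9.7 itself says "The project team will review group level summary results but will not be unblinded at the subject level" and names only the investigators as excluded from interim results. Section 9.2 says "Group summaries will be reviewed by the Sponsor's trial team in order to make scientific decisions for future studies". sSAP 3.2 and 3.7 repeat 9.2 and 9.7. The sSAP Appendix sets up a folder of group summaries that the project team can open, and adds: "The protocol statistician will prepare the Early Results Memo based on the group level summary results using the tables posted in this folder".

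**Who is unblinded.** Protocol 9.2 and sSAP 3.2 state that "Subject-level unblinding will be restricted to the unblinded statistician and unblinded statistical programmer performing the interim analysis", together with the designated sponsor staff who review safety data. Section 9.7 describes the first two as "An unblinded statistician and a statistical programmer who are otherwise not involved in the trial or the project". Section 6.3.3 names one unblinded sponsor role, a Clinical Research Associate who monitors vaccine accountability, and says: "All other Sponsor personnel or delegate(s) directly involved with the conduct of this study will remain blinded to the participant-level intervention assignment". Table 5 in the sSAP Appendix has an access row for "Unblinded statistician / unblinded statistical programmer / unblinded clinical scientist", separate from the row for the safety reviewers.

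**The dry run.** Before the interim lock, the study team reviews trial output produced from the data then available, with dummy treatment codes (sSAP Appendix, TEST region). The Appendix does not say whether antibody results are among those data.

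**The concern.** Read literally, 10.1.4.1 and 9.7 cannot both be obeyed: a team that opens the summary folder follows 9.7 and breaks 10.1.4.1. The labels project team, study team and trial team are used without definition, so the conflict cannot be settled by role. The list of unblinded roles is worded as closed, yet the Appendix adds one, and the requirement to be otherwise uninvolved in the trial is not stated for it.

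The dry run raises a more statistical worry. Only V114 contains serotypes 22F and 33F, so dummy codes would not hide the vaccine from someone who could see an infant's post-vaccination 22F and 33F results. Blinded team members write the memo on per-protocol exclusions before the same lock, and one exclusion criterion is judged case by case. If arm and response could be inferred, those judgements could be biased.

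At stake would be the sponsor's blind, and through it the per-protocol immunogenicity estimates.

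**Working it through.** No figure in the plan is in dispute, so the check is mainly a comparison of texts, followed by a bound on the possible effect.

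**1. Statements on the team's access.**

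| Place | Group summaries go to the team? |
|---|---|
| Protocol 9.1, sSAP 3.1 (interim row) | Consistent with yes: summaries reviewed, study team blinded at subject level |
| Protocol 9.2, sSAP 3.2 | Yes |
| Protocol 9.7, sSAP 3.7 | Yes |
| sSAP Appendix, Table 5 and summary folder | Yes |
| Protocol 10.1.4.1 | No, if read without limit |

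One sentence stands against all the operative text. It closes a section about the subject-level safety review, so it is either a drafting slip or a statement meant for that review alone.

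**2. Does any result depend on which rule is followed?**
- *Under 10.1.4.1,* the team waits. The early memo and the planning of later studies are delayed; the data and final analyses are the same.
- *Under 9.7,* the team sees group-level results after the interim lock. Per-protocol decisions for 1 month post-Dose 3 have by then been made (9.5.1). The unblinded statistician must mask output that could identify an individual, such as events seen in only one participant or one group.
- *Under both,* investigators receive nothing. They and the parents generate the solicited adverse-event data behind the primary endpoints. The plan also states that the interim will not change the conduct of the trial.

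**3. The added role.** The sSAP summary of changes records its addition, sSAP 3.7 points to the Appendix, and the Appendix states its task: telling the unblinded statistician and programmer about any wrong product or route. That task requires knowledge of the allocation, so giving it to an unblinded person protects the blinded team. What remains is a list that was not updated.

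**4. The dry run: size if the worst happened.** Inputs are the planned 36 per arm and the Table 7 intervals for equal proportions (protocol 9.9). Dropping one non-responder from a group with x responders moves its rate from x/36 to x/35. With the other group unchanged, the between-group difference moves by the same amount.

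| x | x/36 | x/35 | Shift (points) | Table 7 half-width | Shift ÷ half-width |
|---|---|---|---|---|---|
| 31 | 86.1% | 88.6% | 2.46 | 17.2 | 0.14 |
| 33 | 91.7% | 94.3% | 2.62 | 14.9 | 0.18 |
| 35 | 97.2% | 100% | 2.78 | 11.9 | 0.23 |

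One wrong exclusion therefore moves the estimate by less than a quarter of the half-width.

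**5. What that would require.** Serology would have to be loaded before the lock, shown by subject and used to infer the arm. A participant would also have to have received a prohibited medication or vaccine before a blood draw, and the judgement on that case would have to be swayed. Case-by-case discretion is stated only for that criterion, so a non-responder cannot simply be removed. The documents establish none of these steps.

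**6. Built-in check.** All three secondary objectives at 1 month post-Dose 3 also have a supportive full-analysis-set analysis by randomised group (protocol Table 4; sSAP Table 1). A per-protocol result distorted by exclusions could be compared with it.

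**The case for a change.** The best argument for acting is that 10.1.4.1 does not say what the charitable reading needs. Section 9.7 has nearly the same closing sentence with only the investigators in it. Section 10.1.4.1 adds the project team and makes no exception for group summaries, so an auditor could record a breach whichever rule staff followed. Likewise, a list worded as closed should be complete, and dummy codes cannot mask an outcome that itself points to the vaccine.

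The textual part stands: the sentence is wrong or too broad, and the two lists lag behind the Appendix. These are matters of document tidiness, because the folder permissions say what will actually be done.

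The dry-run part stands only as a question. The trial runs under in-house blinding procedures (9.2) that are not reproduced here, and they may already withhold serology. How far 22F and 33F values could reveal the vaccine depends on response rates that the documents do not give. Even full visibility would not separate subcutaneous from intramuscular V114. One limit on the reassurance should be conceded: the pre-Dose 4 and post-Dose 4 analyses are per-protocol only, so the full-analysis-set check does not reach them. They are exploratory.

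**Conclusion.** No change to the plan is needed. The access conflict is a clerical slip in one sentence of 10.1.4.1, which the rest of the protocol and the sSAP resolve in the same direction. The missing role is an out-of-date list, not hidden access. Silence on serology in the dry run is a detail that sponsor procedure would ordinarily cover; no leak is shown. Neither access rule changes an endpoint, an estimate or the primary safety analysis, which uses all participants as treated.

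The bound on harm is 2.5 to 2.8 points per wrongly excluded non-responder, against half-widths of 11.9 to 17.2. It assumes 36 evaluable participants per arm, one such exclusion in one group, and response counts in the range of Table 7. The conclusion also assumes that the Appendix permissions and masking are applied as written. It would need revisiting if subject-level post-vaccination 22F or 33F values were found to have been open to the people who wrote the exclusion memo.
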